further for eligibility using the participant eligibility summary (PES). Eligible participants will undergo informed consent procedures and a total of 60 participants will be randomized to the collaborative care intervention (n = 30) or care as usual (n =30) condition. Intervention activity will continue for three months after the ED visit, while follow-up continues for six months after the ED visit. Primary outcomes include feasibility. Secondary outcomes include substance use measured by days of use of opioids as well as utilization of healthcare services including ED visits, primary care visits, mental health visits and substance use treatment visits.

1. Aims and Hypotheses

- 1) The primary aim** of the investigation is to determine the feasibility of the collaborative care intervention initiated from the ED and delivered longitudinally. Taken together, all elements of the intervention are referred to as ED-LINC. Feasibility measures include enrollment rates, retention rates at each outcome and follow-up assessment, intervention completion rates and number and types of contacts made by the interventionist. Feasibility of implementation will also be assessed. Guided by Proctor's taxonomy of implementation outcomes⁷, acceptability, feasibility and fidelity to ED-LINC will be measured.
- 2) The secondary aims** of the study are to determine differences in substance use and health care utilization between the two arms. While the study is not powered to detect a difference as this is a feasibility pilot study, substance use and health care utilization will be measured. Specifically, substance use will be measured utilizing a time-line follow back calendar administered by the research assistant to determine days of heroin or illicit opioid use and days of prescription opioid misuse. Additionally, EDIE will be utilized to determine ED utilization and inpatient admissions across Washington, Oregon, Alaska and other areas that EDIE is active. Participants will provide self-report information on primary care visits, mental health and substance use treatment visits. Engagement in substance use treatment will be confirmed via phone by study staff at all periods of assessment.

2. Participants

a. Inclusion Criteria:

- Aged 18-65
- Patients with at least one risk factor for opioid use disorder via the EMR pre-screen

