Patient-reported outcomes will be assessed at 1, 3 and 6 months after the ED visit. Length of the follow-up interviews varies and is estimated that the shortest interview may take about 15 minutes to complete and up to 60 minutes to complete the longest follow-up assessment depending on subject answers. Subjects will be remunerated for their time. The study team will be flexible with regard to completion method of the follow-up interviews. The study team intends to complete follow-up interviews with subjects primarily in-person at Harborview Medical Center or other convenient public location or over the phone. Responses will be entered into REDCap. If scheduling time with an interviewer is difficult, a subject may also have the option of completing the follow-up assessment through the encrypted REDCap app or web-based platform, or by another preferred method (e.g., faxed interview, hardcopy mailed to their residence). If a subject is completing the assessment on their own, the interview form (e.g., PDF, hardcopy, REDCap) would not include their name or any directly identifying information. Subjects will be given explicit instructions on certain assessments such as the timeline follow back (TLFB) in order to complete this with accuracy and without RA/RC assistance. Subjects will be reminded they should complete the interview in a private space where no one else can have access or see the interview.

Some subjects will have difficulty completing the entire interview, such as due to fatigue. The study team will allow for patients who are unable to tolerate a full-length interview the option of completing an interview over multiple sessions

Prior observations from the study team's effectiveness implementation spectrum investigations suggest flexibility is also required with regards to the timing of outcome assessments. Biostatistical considerations related to power encourage obtaining follow-up assessments, even if the actual assessment date deviates from the planned outcome assessment point. The study team will attempt follow-up on the appropriate date (e.g., within 30 days for the one month follow-up interview) but understand that flexibility on timing of followup interviews are needed.

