Past 30-day substance use will be obtained at baseline and every follow-up assessment and calendar will be used to track substance use on specific days. Prior to performing this assessment, members of the study team will receive training on TLFB methods including a webinar published by NIDA, review of the methods with current NIDA CTN project coordinators that have performed these assessments for a variety of substances in a variety of settings including the ED and will practice obtaining this data with practice participant encounters. This training will be completed prior to study start to ensure accuracy of obtaining this data. Episodic shadowing by study PI will be done to ensure there isn't drift of accuracy in data collection. TLFB data will be captured on a hard copy calendar and transferred to RedCap by study staff. The hard copy will not contain any PHI and be labeled with a study ID and will be kept in a locked cabinet in a locked

office. At least 25% of these forms will be double-entered into RedCap to ensure accuracy of data entry.

- **Health Care Utilization**

Emergency department (ED) utilization will be assessed throughout the duration of the trial using either the UW EMR system (e.g., the UW Amalga data repository) or the Emergency Department Information Exchange (EDIE) web-based platform on an approximately monthly basis. Additionally, EDIE data will be pulled for all consented patients to capture all ED visits, inpatient visits and any available outpatient visits from five years before enrollment up to five years after enrollment in the trial.

- **ED-LINC Intervention and Usual Care**

The study team will document ED-LINC intervention activities in REDCap. These notes are not static and are modifiable over the course of the trial. For instance, information may be added or modified as a consequence of supervision discussion. The study team will review documentation during team meetings and case conference supervisions and update notes as needed to provide the most complete and accurate picture of what transpired. The data logging tool in REDCap allows administrators to track these types of historical changes. REDCap records the date, time, username of the person logged in at that time, the type of event and the changes that were made. This audit trail in the data logging tool stores every entry/change throughout the life of the database which will help the study team check completeness of intervention data.

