The study team will document how many and what type of consults each patient in the usual care (UC) condition receives. This consultation information will be obtained primarily from the EMR and entered in to REDCap. The team will rely on information from the EMR to ensure completeness and accuracy of all UC documented in REDCap

VIII. INTERIM ANALYSIS PLANS

Interim analysis is not relevant as this is a pilot study and effect sizes are not being measured.

IX. CONTENT AND FREQUENCY OF DSM REPORTS TO NIDA

Annually, the PI ([name]) will submit a grant report (RPPR) to NIDA. The grant report is due in June every year and will include details on:

- Study progress which will include details on feasibility measures, secondary outcomes including substance use and health care utilization and any problems reported to the IRB. An enrollment table will be completed per NIH guidelines
- Responsible conduct of research training received

References

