I. STUDY IDENTIFICATION INFORMATION

TITLE OF PROTOCOL: Emergency Department Longitudinal Integrated Care 2.0 (ED-LINC 2.0)

PRINCIPAL INVESTIGATOR: [name] MD MS

FUNDER OF PROTOCOL: National Institute of Drug Abuse (NIDA)

CLINICALTRIALS.GOV: A description of this clinical trial will be available on <http://www.clinicaltrials.gov>, as required by U.S. Law. **NCT03699085**

SAP Version date: September 2021

Table of Contents:

Summary of Clinical Trial Features.....	Page 3
Primary Outcome Measures.....	Page 4
Refusal Rates	
Follow-up Completion Rates	
ED-LINC Intervention and usual Care process Outcomes	
Implementation Appropriateness	
Satisfaction	
Perception of Care Coordination	
Secondary Outcome Measures.....	Page 5
Substance Use	

Summary of Clinical Trial Features:

The *Emergency Department Longitudinal Integrated Care* (ED-LINC) intervention is a stepped collaborative care model of care initiated from the ED for patients with OUD that combines evidence-based treatment elements, proactive care coordination and population-level outcome tracking. ED-LINC builds upon previous work by tailoring the collaborative care model for patients at high risk for OUD presenting to the ED. A central objective of ED-LINC is to provide evidence-based treatment for OUD and related co-morbidity while in the ED in conjunction with proactive longitudinal care coordination that links patients to ongoing treatment. Weekly caseload supervision with measurement-based care outcome tracking allows for the stepping up of care for patients with recalcitrant symptoms, as well as opportunities to oversee care management linkages to community services targeting the key outcomes of initiation of MOUD and retention in MOUD treatment.

The main objective of this study was to conduct a pilot pragmatic randomized clinical trial of ED-LINC (n=20) compared to usual care (n=20) for ED patients at a single-site at high risk for OUD. The primary outcomes of this study pertain to feasibility of the model, research strategy and implementation.

Primary Outcome Measures

All primary outcome measures used **descriptive statistics**

Refusal Rate was calculated as the number of patients that refused or declined the self-report screening procedure in the ED divided by the eligible number of patients that could have done the self-report screening during the enrollment period.

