Follow-up Completion Rates were calculated for each followup timepoint and were calculated as the number of participants that completed follow-up divided by the total number of participants randomized to each arm of the trial. The 6-month followup completion rate is shown as the number of participants that completed the 6-month self-report interview divided by the number of participants randomized to each arm.

ED-LINC Intervention and usual Care process Outcomes were determined from extensive research notes. Specifically the EDLINC interventionist conducted a process validity assessment and documented the number of unique ED-LINC elements completed for each participant in the intervention.

Implementation Appropriateness was calculated by providing this validated self-report measure to each participant randomized to the ED-LINC assessment. Results were dichotomized to calculate the frequency of participants who 'agreed' or 'completely agreed' that the intervention was 'applicable' and 'seemed like a good match' to document appropriateness.

Satisfaction was calculated using a validated satisfaction questionnaire and provided to all participants at six-months. Each participant will complete the questionnaire and their results will be summed. The median and IQR range will be calculated for participants in each group that complete the assessment.

Perception of Care Coordination will be done using questions from a validated scale. The Wilcoxon Rank Sum test will be used to determine if there are significant differences between groups.

Secondary Outcome Measures

Substance Use

Substance use will be measured using the timeline follow back procedure which is a validated calendar method to determine days of use in a certain calendar period. First, we will sum days of use of illicit opioid use in 30 days at baseline and each followup period for each participant. The mean days of use/30 days with an associated standard deviation will be calculated at each time-period for both the ED-LINC intervention and the usual care control groups.

Next, we will evaluate variance of the data and test model fit on unadjusted data using different distributions. Given previous work, we anticipate the data to be skewed and zero-inflated. Thus, we hypothesize that we may use a normal Gaussian, Poisson or negative binomial distribution.

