Once model fit is determined, a reverse stepwise selection will be performed using a linear regression of clinician-selected input variables, alongside the intervention and TLFB timepoint, and an elimination threshold of $p > 0.05$

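### The SAP's only regression takes up to four opioid-use reports per participant and names no within-participant term; fitted literally, it overstates certainty about arm and person-level covariates

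*SAP*

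**What the plan says.** - **Outcome.** In the SAP, Substance Use, the first step is "we will sum days of use of illicit opioid use in 30 days at baseline and each followup period for each participant". Means and SDs by arm and period follow.
- **Timing.** Protocol III, Follow-up Interviews: "Patient-reported outcomes will be assessed at 1, 3 and 6 months after the ED visit". Protocol VII.B.2, Substance Use and TLFB: "Past 30-day substance use will be obtained at baseline and every follow-up assessment". That makes four planned measurements per person.
- **Distribution.** The SAP says "we anticipate the data to be skewed and zero-inflated" and lets model fit choose between Gaussian, Poisson and negative binomial.
- **Regression.** The last sentence of the SAP describes reverse stepwise selection "using a linear regression of clinician-selected input variables, alongside the intervention and TLFB timepoint", with terms removed at p > 0.05. It is the only regression in either document.
- **Purpose.** The secondary aim (Protocol II.B.1) is "to determine differences in substance use and health care utilization between the two arms", and the same item says the study is not powered for this. Protocol VIII gives as its reason for having no interim analysis that "this is a pilot study and effect sizes are not being measured".

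Neither document mentions a random effect, GEE, clustered standard error or repeated-measures covariance. Nor do they say whether baseline is an outcome row, whether arm and timepoint are exempt from elimination, or whether the regression is the selection step or the final model.

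**The concern.** Timepoint can be a regressor only if a participant's measurements enter as separate rows. Repeated reports of opioid use from one person are very likely to be positively correlated. Ordinary regression treats them as independent, so it counts too much information for anything that is constant within a person, such as arm or a baseline covariate. For comparisons within a person, such as timepoint, it usually counts too little. Choosing a distribution deals with the shape of the outcome, not with this dependence.

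Both readings of the SAP sentence are affected. If it is the final model, the arm p-value and interval overstate certainty. If it is only the selection step, covariates are kept or dropped on wrong p-values and the final model is unnamed. An arm interval that is too narrow could mislead the planning of the later ED-LINC studies that this pilot is meant to inform.

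**Working it through.** The documents give no SD, effect size or within-person correlation for this outcome, so there is no figure of the plan's own to reproduce.

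**Inputs from the documents.** 20 per arm (SAP, Summary of Clinical Trial Features; the protocol says 30); 80% retention at each follow-up (Protocol II.B.3); four timepoints; elimination at p > 0.05.

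**Assumed.** Within-person correlation ρ from 0.1 to 0.7, exchangeable unless stated; baseline complete; a two-sided 5% test of arm, if one is reported.

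**Arm, by formula.** With baseline as a row, rows per person are m = 1 + Bin(3, 0.8).

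- E[m] = 1 + 2.4 = 3.4
- E[m²] = 3.4² + 3 × 0.8 × 0.2 = 11.56 + 0.48 = 12.04
- Design effect DE = 1 + (12.04/3.4 − 1)ρ = 1 + 2.54ρ
- True error = 2 × [1 − Φ(1.96/√DE)]

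At ρ = 0.5, DE = 2.27, √DE = 1.507 and 1.96/1.507 = 1.301, so the error is 19.3%.

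With follow-up rows only, m = Bin(3, 0.8), E[m] = 2.4 and E[m²] = 5.76 + 0.48 = 6.24. Then DE = 1 + (6.24/2.4 − 1)ρ = 1 + 1.6ρ.

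**Timepoint, by formula.** With equal rows per person, the true SE divided by the ordinary-regression SE is √(1 − ρ), so the error is 2 × [1 − Φ(1.96/√(1 − ρ))].

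| ρ | Arm, all rows: formula | Arm, all rows: simulation | Arm, follow-up rows: formula | Timepoint: formula |
|---|---|---|---|---|
| 0.1 | 8.0% | about 8% | 6.9% | 3.9% |
| 0.3 | 14.0% | 13-15% | 10.7% | 1.9% |
| 0.5 | 19.3% | 17-20% | 14.4% | 0.6% |
| 0.7 | 24.0% | 22-25% | 17.8% | 0.03% |

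The simulations used ordinary least squares on arm and timepoint, 20 per arm and 80% retention. Outcome shapes included bounded 0-30-day data with 25% at each end and a skewed shape with 50% zeros. At zero correlation the arm error was about 5%. With 30 per arm at ρ = 0.5 it was 19.0%, so the difference in sample size between the documents does not matter here.

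**Covariate elimination.** With 3, 6 or 10 pure-noise person-level candidates (number assumed; 25%-at-each-end shape only), each one survived in 8-10%, 15-16%, 20-24% and 25-30% of trials at ρ = 0.1, 0.3, 0.5 and 0.7. At zero correlation it was 5-6%.

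**Where the direction changes.**

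- *Autocorrelated errors.* Under AR(1) with monthly correlation 0.8 and linear time, the timepoint error is 4.3%, close to nominal. Arm is still at 20.6%.
- *Arm-by-time term, ρ = 0.5.* The arm coefficient becomes the baseline difference and its test is at 5.0%. The interaction tests are too conservative, at about 0.8%.
- *Naive Poisson.* Overdispersion dominates. A null timepoint was rejected in 61-85% of trials across two outcome shapes at ρ of about 0.3 to 0.7.
- *Timepoint open to elimination.* With an assumed real fall of 5 days after baseline in both arms, least squares drops timepoint in 66%, 70% and 77% of trials at ρ = 0.3, 0.5 and 0.7. A participant-level model drops it in 47%, 29% and 8%. These figures do not arise if timepoint is forced in.

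**The case against.** The strongest reply is that the fault is under-specification, not a wrong model. The sentence reads most naturally as a variable-selection step, so no arm estimate or interval is shown to be wrong. The documents never say that errors are treated as independent. The sentence also ends without a full stop, so silence should not be read as a deliberate choice. The primary outcomes are descriptive feasibility measures and the trial is openly unpowered.

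Most of this stands, and it limits the point. A reader might infer that the trial has a false-positive rate of 20% or more for its treatment effect. The documents do not support that: no 5% test of arm is stated and the correlation is unknown. A reader might also infer that real change over time, or arm itself, will be wrongly eliminated or retained. That requires those terms to be open to elimination, and the SAP's wording may equally mean that they stay in. Nor can it be said that timepoint always errs on the conservative side, because the SAP allows a Poisson fit, although a proper fit check should reject a naive one.

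What does not stand is the view that nothing needs changing. An analyst who follows the sentence literally fits ordinary regression, and the p > 0.05 rule then acts on wrong p-values for person-level covariates even if the step is only selection.

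**Conclusion.** The concern holds, conditionally. As ordinary linear regression with main effects, the SAP's only regression overstates certainty for arm and person-level covariates. At assumed correlations of 0.1 to 0.7, the arm error is about 8% to 25% with all rows and about 7% to 18% with follow-up rows only. The direction for arm needs only positive within-person correlation; the size depends on a correlation that the documents do not give. The timepoint test is usually too conservative under exchangeable correlation. That finding does not extend to naive Poisson and can nearly vanish under AR(1) with linear time. The arm result does not apply if an arm-by-time term is added.

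The consequences stay within an exploratory secondary outcome. The means and SDs by arm and period, and the feasibility outcomes, are untouched. It should be fixed, because the repair is cheap, but it does not threaten the trial's main purpose.

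**What to change.** State whether the regression is the selection step or the final model, and replace it with:

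> TLFB days at 1, 3 and 6 months will be modelled with a Gaussian mixed model with a participant random intercept, or by Gaussian or Poisson GEE with participant-clustered, small-sample-corrected standard errors. Arm, timepoint and baseline TLFB days stay in the model and are exempt from elimination. Any covariate selection uses the same participant-level model. Tests of person-level terms use a t reference with degrees of freedom equal to participants minus the number of person-level parameters fitted, including the intercept and any retained covariates. The arm difference is reported with a 95% CI, labelled exploratory, and noted as not adjusted for the selection step.

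Baseline days are there for precision; validity does not require them.

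**Tested.** With 20 per arm, 80% retention, correlation 0.1-0.8 and both outcome shapes, arm error was 4.5-5.8% (Gaussian mixed model), 3.8-5.3% (Gaussian GEE) and 3.2-4.7% (Poisson GEE). Monte Carlo error was about ±1.2 points. These runs had no selected covariates, so the person-level parameters were intercept, arm and baseline, giving 40 − 3 = 37 degrees of freedom. Performance after stepwise selection was not tested.

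**Caution.** Negative binomial GEE reached 6.1-6.8% in the 50%-zeros shape, and a negative binomial mixed model was not tested. Use a negative binomial version only after its error rate has been checked by simulation.

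**Cost.** SAP wording and a few lines of code, with no new data. The interval is usually wider: the mean 95% half-width for arm was 5.5, 5.6, 5.4 and 4.6 days at correlations of 0.1, 0.3, 0.5 and 0.7, against 4.1 for the literal all-rows fit. At 0.8 it was 3.9, where the baseline covariate more than offsets the correction.

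### The SAP's opioid-use model has a single arm term, no arm-by-timepoint contrast and no stated role for baseline use, so its estimate is either diluted by the pre-treatment month or averaged over on- and post-intervention visits

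*SAP*

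**What the plan says.** The secondary aim in the Protocol (II.B.1, Aims and Hypotheses) is to "determine differences in substance use and health care utilization between the two arms". On timing, Protocol II.B states: "Intervention activity will continue for three months after the ED visit, while follow-up continues for six months after the ED visit". Interviews are at 1, 3 and 6 months (Protocol, Follow-up Interviews), and each TLFB covers the past 30 days (Protocol VII.B.2).

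In the SAP, under Substance Use, the analysis has three parts:

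- **Summary.** The SAP will "sum days of use of illicit opioid use in 30 days at baseline and each followup period for each participant". It adds: "The mean days of use/30 days with an associated standard deviation will be calculated at each time-period for both the ED-LINC intervention" group and for usual care.
- **Distribution.** Skewed, zero-inflated data are expected, and "we may use a normal Gaussian, Poisson or negative binomial distribution".
- **Model.** Once fit has been judged, "a reverse stepwise selection will be performed using a linear regression of clinician-selected input variables". Arm and timepoint enter in the second half of that sentence, which also sets the cut-off for removal at p > 0.05: "alongside the intervention and TLFB timepoint, and an elimination threshold of".

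The SAP specifies no more of the model than this. It names no arm-by-timepoint term, target visit or contrast. It does not say whether baseline days are an outcome row, a covariate or neither, and it does not list the clinician-selected variables. It does not exempt the arm term from elimination.

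**The concern.** The TLFB periods differ in kind. Baseline precedes any treatment, the 1- and 3-month windows fall broadly within the planned three months of ED-LINC, and the 6-month window falls after it. When arm and timepoint enter only as main effects, one arm coefficient is fitted across whichever periods are rows in the model.

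If baseline is a row, that coefficient includes a period in which ED-LINC cannot have acted, so it is pulled toward zero. If baseline is not a row, it is an average over follow-up, which matches the effect at each visit only if the effect is constant.

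This is a question of what the point estimate targets. It is separate from how repeated rows from one participant affect the standard error. At stake is the modelled answer to the secondary aim, and any effect size carried from this pilot to a later trial. A coefficient that has been pulled toward zero is also more likely to be removed by the p > 0.05 rule, which would leave no modelled arm comparison.

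**Working it through.** The documents give no effect size, SD or power for this outcome, so there is no planned figure to reproduce. The check asks what the arm term is expected to estimate.

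**Inputs**
- Periods: baseline, 1, 3 and 6 months (SAP, Substance Use; Protocol, Follow-up Interviews).
- Attrition at follow-up: about 20% (Protocol, Follow-up Interviews).
- Allocation: equal arms, 20 per arm in the SAP and 30 per arm in the Protocol. The fractions below do not depend on n.
- Assumed: identity link, equal retention in the two arms, and an expected arm difference of zero at baseline.

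**Formula.** With arm and timepoint as main effects and equal arms at each visit, the expected arm coefficient is the row-weighted mean of the visit differences d_t:

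E(b) = Σ n_t d_t / Σ n_t

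The weights are 1 : 1 : 1 : 1 with complete data, and 1 : 0.8 : 0.8 : 0.8 with 20% attrition.

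**Share of a true effect d recovered**

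| Effect present at | Baseline a row, complete | Baseline a row, 20% attrition | Baseline not a row |
|---|---|---|---|
| 1, 3 and 6 months | 3/4 = 75% | 2.4/3.4 = 71% | 3/3 = 100% |
| 1 and 3 months only | 2/4 = 50% | 1.6/3.4 = 47% | 2/3 = 67% |
| One visit only | 1/4 = 25% | 0.8/3.4 = 24% | 1/3 = 33% |

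The last column is unchanged by equal attrition at the three visits.

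**In days.** For an assumed true effect of 6 fewer days per 30, with baseline a row and 20% attrition, the arm term would be expected to show 6 × 0.706 = 4.2 days if the effect is sustained. It would show 6 × 0.471 = 2.8 days if the effect is present only at 1 and 3 months.

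**Simulation check.** 400 trials were simulated with 20 per arm, 80% retention, within-person correlation 0.5 and a true effect of −1.0 SD at 1 and 3 months only. The main-effects arm term averaged −0.47. Arm-by-visit contrasts averaged −0.02 at baseline, −0.99 at 1 month, −0.99 at 3 months and 0.00 at 6 months.

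**Exposure to elimination (illustration).** Assume an effect of 0.8 SD at 1 and 3 months only, 20 per arm, complete data, correlation ρ, a normal approximation and two-sided 0.05. The standard error is √(2V/20), with V as follows.
- Four-period arm term: V = (1 + 3ρ)/4. At ρ = 0.5, V = 0.625, SE = 0.25, 0.40/0.25 = 1.6 and power is 0.36. Over ρ = 0.3 to 0.7, power falls from 0.45 to 0.30.
- Baseline-adjusted mean of months 1 and 3: V = (1 + ρ)/2 − ρ². At ρ = 0.5, V = 0.50, SE = 0.224, 0.80/0.224 = 3.58 and power is 0.95. Over the same range, power rises from 0.92 to 0.99.

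This comparison combines dropping the baseline row, choosing the window and adjusting for baseline. It also assumes that within-person correlation is handled, which the SAP does not state. It shows direction only and does not predict how often the arm term would be eliminated.

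**The case against.** The strongest reply is that the SAP states no pooling rule. Its sentence describes variable selection and does not give a final model. The summing of baseline days may serve only the descriptive means, and baseline use could be among the unlisted clinician-selected variables. This stands: the defect is under-specification, and the dilution belongs to the natural reading.

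A reader might infer that any effect must be diluted. The documents do not support that, because without baseline rows a sustained effect is recovered in full and a follow-up average is a legitimate quantity. A reader might also infer that the plan cannot show when an effect occurs. That goes too far as well: means and SDs by arm and period show timing descriptively. What is missing is a modelled, baseline-adjusted contrast with an interval.

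Three further points stand in part:
- The percentages assume an identity link. The selection step says linear regression, but Poisson and negative binomial are also candidates. With a log link the averaging is on the ratio scale and the figures change.
- The periods are not sharply separated. The Protocol lets intervention activity run past three months (End of Study Participation) and allows flexible interview timing (Follow-up Interviews).
- This is a secondary outcome in a pilot declared not powered for it (Protocol II.B.1), and Protocol VIII says effect sizes are not being measured. That lowers the severity. It excuses imprecision, but not an estimate aimed at a mixture of periods when the stated aim is a difference between arms.

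**Conclusion.** This should be fixed; confidence is moderate. Followed as written, the model gives one arm term that is either diluted by the pre-treatment month (75% of a sustained effect and 50% of one confined to 1 and 3 months; 71% and 47% with 20% attrition) or averaged over follow-up (100% and 67%). These figures rest on a linear identity-link model, equal retention in the arms and no expected baseline difference. Which case applies cannot be settled from the SAP. In either case no arm contrast by visit with an interval is planned, and the arm term can be eliminated.

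It would be tempting to treat this as an error that invalidates the trial's result. The documents do not support that: the primary outcomes are feasibility measures, and this model does not affect them.

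**What to change.** Amend the SAP's Substance Use section as follows:

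1. Use only the 1-, 3- and 6-month TLFB values as outcomes, with each participant's baseline TLFB days as a covariate. Alternatively, keep baseline as an outcome with a common mean in both arms.
2. Include arm-by-timepoint, and report the adjusted arm difference with a 95% interval at each visit. A follow-up average may be added.
3. Keep arm, timepoint, their interaction and baseline days out of the stepwise elimination.
4. Reconcile the order of baseline and randomisation. Protocol III.D and III.E place randomisation and disclosure of the assignment before the baseline interview, whereas Appendix C places baseline collection before randomisation. Report the order actually followed, because the adjustment relies on baseline reports being unaffected by knowledge of the arm.

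The cost is SAP wording and a re-run on TLFB data that the Protocol already collects. The downside is that estimates by visit are less precise than one figure averaged over follow-up, in a pilot not powered for this outcome.
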